HRP-503B – BIOMEDICAL RESEARCH PROTOCOL
(2017-1)

Protocol Title: Guanfacine to Improve Substance Use Outcomes in Women
HIC#: 2000023100

Principal Investigator: [name] PhD

Version Date: April 2018

(If applicable) **Clinicaltrials.gov Registration #:** Click or tap here to enter text.

SECTION I: RESEARCH PLAN

- Statement of Purpose:** State the scientific aim(s) of the study, or the hypotheses to be tested.

We hypothesize that Guanfacine (GUA) (3mg/day) will reduce drug craving, improve cognitive flexibility and result in associated lower drug use in women with substance use disorder (SUD) in an outpatient clinical setting. This study proposes to extend our previous Phase I experimental work to address the following specific aims: (1) assess GUA's target engagement of drug craving and cognitive flexibility in a laboratory challenge session and in a 10-week outpatient clinical study, (2) demonstrate target validation by showing that reduced drug craving and improved cognitive flexibility will predict lower drug use outcomes during the 10-week clinical trial in SUD women, and finally, (3) evaluate data replication and scalability of GUA target effects across two clinical sites (Yale and SUNY-Stony Brook).

- Probable Duration of Project:** State the expected duration of the project, including all follow-up and data analysis activities.
3 years followed by 2-years data analysis
- Background:** Describe the background information that led to the plan for this project. Provide references to support the expectation of obtaining useful scientific data.

Growing basic evidence indicates that the alpha-2 adrenergic agonist, guanfacine (GUA) decreases drug-related striatal-limbic up-regulation and stress sensitization resulting in drug cue and stress-induced reinstatement in laboratory animals (Shaham and Hope, 2005), and also improves neurocognitive abilities such as attention, flexibility, working memory and decision making (Arnsten, 2009). In NIDA-supported medications development work (R01-DA027130, PI: [name]), we identified in a 3-day inpatient laboratory controlled experiment that GUA at 3mg/day dose engaged target drug craving and cognitive flexibility processes, and more importantly, that GUA engaged these key processes in a sex-specific manner with

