The schedule of the laboratory challenge tests at pre-treatment in Week 0 and in week 8-9 is shown in Table 2 below. Each laboratory session will take place over 2-hours in one afternoon, and comprise exposure to 3, 5-minute personalized imagery conditions (stress, neutral, drug cue), presented in a randomized and counterbalanced order. In each case, all participants will be brought into the testing room at 2:45 PM. If needed, a smoke break will be given to control for nicotine withdrawal. An ambulatory EKG (Holter) monitor will be used to record vitals and heart rate variability (HRV). After 10 minutes relaxation, drug craving, anxiety, mood, HRV and saliva will be collected at -10 and -5 minutes prior to imagery exposure. Subjects will then be given headphones and asked to imagine the situation being described, 'as if' they were actively participating in it at that moment. The script will be presented for exactly 5 minutes. All measures will be collected again immediately following imagery (0) and at +15 and +30 minutes recovery. The Stroop task will be administered at baseline and following imagery only. All participants will have 10 minutes of relaxation in between each of the three imagery sessions. All saliva will be placed on ice immediately, prior to storing at -80. Relaxation instructions will be provided following exposure to all three imagery conditions in order to ameliorate any potential residual effects of stress. All staff and participants will be blind to the order of imagery presentation. Imagery script development, imagery training and relaxation techniques will be

conducted in the week prior to the laboratory sessions as per prior research ([name] et al., 1999; [name] et al., 2000; [name] et al., 2003) (Fox et al., 2008; Fox et al., 2005; [name] et al., 2006; [name] et al., 2011) and our standardized imagery procedures manual ([name] and Tuit, 2012).

Table 2. Laboratory Experimental Protocol (Exactly same for each of the two laboratory sessions).

2:45 PM	Subject arrived; urine and BAC check Psychophysiological setup
Stress / Drug Cues (Condition 1)	
3:00 PM	BASELINE PERIOD; on-line heart rate and anxiety ratings
3:05 PM	Craving and DES ratings; Cortisol samples
3:10 PM	IMAGE PERIOD; on-line heart rate and anxiety ratings
3:15 PM	Craving and DES ratings; Cortisol samples
3:20 PM	RECOVERY PERIOD; on-line heart rate and anxiety ratings
3:25 PM	Craving and DES ratings; Cortisol samples
3:30 PM	10-minute Relaxation Period

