Neutral Imagery Condition (Condition 2)	
3:40 PM	Schedule as in condition 1
Stress / Drug Cues (Condition 3)	
4:20 PM	Schedule as in condition 1

Order of imagery conditions is counterbalanced across subjects.

Study Assessments: Assessments include the following:

- 1) Sample description and eligibility including sociodemographics; psychosocial, substance use, and medical history; psychiatric assessment using the:
 - i) Structured Clinical Interview of Diagnostics (SCID-I) for DSM-V,(First et al., 1995),
 - ii) Connors ADHD Assessment and Rating Scale (CAARS,(Conners, 1999)
 - iii) vitals
 - iv) CBC, blood chemistry
 - v) urinalysis
 - v) pregnancy testing;
- 2) Primary SUD outcomes assessed using the:
 - i) Substance Use Calendar (SUC) developed by Miller and Del Boca (Miller and Del Boca, 1994) and based on the Time-Line Follow-Back (Sobell and Sobell, 1992; Sobell et al., 1996) and urinalysis for objective drug use assessed 2X/weekly during the 10 week period (20 urines);
- 3) Secondary Outcome Measures assessing drug craving using the standard brief versions of the Drug Craving questionnaires for cocaine (Cocaine Craving Questionnaire: CCQ,(Tiffany et al., 1993), cannabis (Marijuana Craving Questionnaire: MCQ, (Heishman et al., 2009)), alcohol (Alcohol Urges Questionnaire: AUQ, (Bohn et al., 1995) and nicotine (Questionnaire of Smoking Urges: QSU(Tiffany et al., 1993); (Tiffany and Drobes, 1991). Drug abstinence symptoms using standardized cocaine selective severity assessment (CSSA, (Kampman et al., 1998), Clinical Alcohol Withdrawal Assessment-Revised (Sullivan et al., 1989); The Cannabis Withdrawal Scale (Allsop et al., 2011); and the Minnesota Nicotine Withdrawal Scale (MNWS; (Hughes et al., 1986). Other drug use and drug related problems will be measured using the SUC; urinalysis; breathalyzer; the Addiction

Severity Index (ASI; (McLellan et al., 1992)) and Treatment Services Review (McLellan et al., 1992); stress (Perceived Stress Scale; (Cohen et al., 1983)); anxiety (Hamilton Anxiety Rating Scale, Ham-A; (Hamilton, 1960)) and depressive symptoms (Hamilton Depression Rating Scale, Ham-D, (Hamilton, 1960)). cognitive flexibility will be assessed using the Stroop Color Word Test; (Golden, 1975),

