Data Management: Data entry will be conducted using the Web-based REDCAP direct data entry system. Both sites are fully trained and running with REDCAP and have implemented this platform in clinical outcome studies with SUD samples. Utilizing the REDCAP system will allow data to be directly collected into the Yale managed web-based system across sites with no identifying information transmitted over the internet. Field validation (e.g. no out of range/invalid responses accepted) and form validation (e.g. logically impossible responses to different questions) are built into the REDCAP system and the study data manager will conduct weekly quality control and data management. After online reviews, the data are archived onto servers and password protected with only certain members of the team having appropriate level of data access. All quality control and management issues will be addressed immediately and also discussed in the across site weekly study meetings.

Data Analysis: Data analysis will be performed under the direction of Project PIs in consultation with [name], the Yale biostatistician. Screening for data entry errors, outlier checks and assessment of missing data and testing of normality assumptions will be conducted. Transformations will be applied as necessary. We will compare the treatment groups on demographic and clinical variables using t-tests/chi-square analyses as appropriate. If any group differences are found, the specific variable will be entered as a covariate in all specific analyses. For the primary outcome, we will use significance level of 0.05. Significance levels for secondary outcomes will be adjusted using Bonferroni correction for number of analyses performed.

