Adequacy of Sample Size: Sample size estimates are limited by the fact that there are no previous clinical outcome studies of GUA/PBO in SUD women. As shown in above, data from our previous work with GUA yielded highly significant sex X med group effects for target engagement measures of drug craving and Stroop improvements with moderate to high effect sizes (f^2 's ranging from 0.39-1.22). Using the GUA/PBO preliminary data from the 8-week pilot trial, percent of negative cocaine urines were 40.18% versus 67.86% in PBO vs GUA for the whole group (large effect size $d=0.76$), with 53.12% versus 100% for PBO vs. GUA in women ($d=1.0$) and 35% vs 55% negative urines in placebo vs guanfacine in men ($d=0.628$). Thus, assuming power=0.80, and at $p<0.05$, α level of 0.05, sample size estimates indicate that we will need 40 subjects per cell (Medgroup) to assess GUA/PBO in clinical outcome hypotheses in Aim 2 and Aim 3. This sample size allows for detection of medium effect sizes ($f=0.25$, Cohen) with more than 80% power assuming α level of 0.05 for the main effect of medication group on the primary outcome variable. Assuming an α level of 0.01 to correct for multiple tests for the secondary outcome measures we can detect effects in the medium range ($f=0.28$) with 80% power for all the main effects for secondary outcome variables. Including a 20% attrition rate, we propose an N=50 per group for a total N of 100 (50 per site).

SECTION II: RESEARCH INVOLVING DRUGS, BIOLOGICS, RADIOTRACERS, PLACEBOS AND DEVICES

If this section (or one of its parts, A or B) is not applicable, check off N/A and delete the rest of the section.

A. RADIOTRACERS

N/A

B. DRUGS/BIOLOGICS **N/A**

1. If an **exemption from IND filing requirements** is sought for a clinical investigation of a drug product that is lawfully marketed in the United States, review the following categories and complete the category that applies (*and delete the inapplicable categories*):

Exempt Category 1: The clinical investigation of a drug product that is lawfully marketed in the United States can be exempt from IND regulations if all of the following are yes:	
1. The intention of the investigation is NOT to report to the FDA as a well-controlled study in support of a new indication for use or to be used to support any other significant change in the labeling for the drug.	

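### With 40 women per arm, the stated inputs give about 60% power at f=0.25 (plan: more than 80%) and 45% at f=0.28, alpha 0.01 (plan: 80%)

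*Combined protocol and SAP*

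**What the plan says.** The sample size paragraph (Section I, item 13, Adequacy of Sample Size) first cites pilot effect sizes. From these it concludes, at 80% power and alpha 0.05, that "we will need 40 subjects per cell (Medgroup) to assess GUA/PBO in clinical outcome hypotheses in Aim 2 and Aim 3". It then makes two statements about sensitivity for a main effect of medication group:

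- Primary outcome: "This sample size allows for detection of medium effect sizes ($f=0.25$, Cohen) with more than 80% power assuming α level of 0.05".
- Secondary outcomes, at alpha 0.01: "we can detect effects in the medium range ($f=0.28$) with 80% power for all the main effects for secondary outcome variables".

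Forty per group is then raised to 50 per group, 100 in total, for 20% attrition.

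Neither this paragraph nor the Data Analysis paragraph before it names the test or model for the outcomes, its sidedness, the number of assessments per woman that enter the analysis, or a correlation. The only rule on covariates is "If any group differences are found, the specific variable will be entered as a covariate in all specific analyses".

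**The concern.** For two equal groups, Cohen's f is half the standardized difference d, so f=0.25 is d=0.50 and f=0.28 is d=0.56. Forty per group is well short of the usual requirement for 80% power at d=0.50, and the stricter alpha of 0.01 costs more than the small rise from 0.50 to 0.56 gives back.

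The paragraph is the protocol's only statement of what the trial can detect. A reader who trusts it would take a null result as evidence against a medium effect. If the stated inputs are the whole calculation, a true f=0.25 would be missed about 40% of the time on the primary outcome, and a true f=0.28 about 55% of the time on each secondary outcome.

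**Working it through.** **Inputs** (all from Adequacy of Sample Size): two groups, 40 evaluable per group (N=80); f=0.25 with alpha 0.05; f=0.28 with alpha 0.01; target power 80%. Sidedness is not stated; I take two-sided first.

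**Method.** F-test with 1 and N−2 degrees of freedom and noncentrality λ = N·f². This is the same as the two-sided two-sample t-test with d = 2f.

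- Primary: λ = 80 × 0.25² = 5.00; critical F(1, 78) at 0.05 = 3.96; power = **59.8%**.
- Secondary: λ = 80 × 0.28² = 6.27; critical F(1, 78) at 0.01 = 6.97; power = **45.0%**.

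The plan's figures are therefore not reproduced. I then tried other readings that use only stated quantities:

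| Reading | f=0.25, alpha 0.05 | f=0.28, alpha 0.01 |
|---|---|---|
| Protocol's claim | more than 80% | 80% |
| 40 per arm, two-sided | 59.8% | 45.0% |
| 40 per arm, one-sided | 71.6% | 55.4% |
| 50 per arm (no attrition), two-sided | 69.7% | 57.0% |
| 50 per arm, one-sided | 79.9% | 66.8% |

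Forty in each of four arm-by-site cells (N=160) would give 88.2% and 82.3%, but the protocol defines the cell as the medication group and enrols 100.

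**What 80% power requires (two-sided).** 64 evaluable per arm for f=0.25 at alpha 0.05, and 77 per arm for f=0.28 at alpha 0.01. With 40 per arm, the detectable effects are f=0.317 (d=0.63) and f=0.390 (d=0.78).

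**What unstated assumptions would rescue the claims.** λ would have to grow by a factor of 1.61 (primary) or 1.94 (secondary).

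*(a) Averaging m assessments per woman, with f defined on one assessment.* λ = N·f²·m / (1 + (m−1)ρ), where ρ is the within-person correlation. Study Assessments (Section I, item 4) plans "urinalysis for objective drug use assessed 2X/weekly during the 10 week period (20 urines"), so m=20 is natural for the primary outcome. The largest ρ that reaches 80% is 0.60 (primary) or 0.49 (secondary).

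For the laboratory outcome, "The Stroop task will be administered at baseline and following imagery only". I read this as 4 to 6 administrations per session: one baseline plus three post-imagery, or a pair for each of three conditions. On that reading the secondary claim needs ρ of at most 0.35 (m=4) to 0.42 (m=6).

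*(b) Adjustment for a baseline value.* λ = N·f² / (1 − r²), with one degree of freedom lost. The smallest r that reaches 80% is 0.62 (primary) or 0.70 (secondary).

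| Assumed model | Correlation | Primary | Secondary |
|---|---|---|---|
| 20 assessments | ρ=0.3 | 97% | 95% |
| 20 assessments | ρ=0.5 | 86% | 79% |
| 20 assessments | ρ=0.7 | 74% | 63% |
| Baseline-adjusted | r=0.5 | 72% | 60% |
| Baseline-adjusted | r=0.6 | 79% | 69% |
| Baseline-adjusted | r=0.7 | 87% | 80% |

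**Two linked inputs.**

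- *Aim 3.* The Statement of Purpose gives this aim as to "evaluate data replication and scalability of GUA target effects across two clinical sites". With 50 women per site, 20% attrition and arms balanced within site, each site has about 20 evaluable per arm. Power within one site at f=0.25, alpha 0.05 is 34%.
- *Pilot rates.* The sample size paragraph says "percent of negative cocaine urines were 40.18% versus 67.86% in PBO vs GUA for the whole group". Section II, B.2 gives the pilot arms as 5 men and 2 women on guanfacine, 4 men and 3 women on placebo. If everyone contributes equal numbers of urines, the sex-specific rates reproduce the guanfacine figure: (5×55 + 2×100)/7 = 67.86%. For placebo they give (4×35 + 3×53.12)/7 = 42.77%, not 40.18%. A 5/2 split gives (5×35 + 2×53.12)/7 = 40.18%. The documents do not show which entry is wrong.

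**The case against.** The strongest reply is that the trial is a repeated-measures design and the protocol never says the test uses one value per woman. The two claims also fit together under a single gain: the factor of 1.94 that brings the secondary claim to 80% gives about 87% for the primary, which agrees with more than 80%. This is a plausible origin for the figures. It does not make them follow from the plan, because the model and the correlation are nowhere stated and the result depends heavily on them. The only covariate rule is triggered by an observed group difference, so it is not planned baseline adjustment.

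A second reply is that 40 per arm does follow from the paragraph. At d=0.628, the smallest pilot effect listed, the normal approximation gives 2 × (1.96 + 0.84)² / 0.628² ≈ 39.8 per arm. That is correct, although it is the men's effect in a trial of women. It supports the N and leaves the two medium-effect statements unsupported.

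A third reply stands as a caution. Data Analysis requires Bonferroni correction for the number of secondary analyses, and 0.01 corresponds to five tests. Study Assessments lists about 14 secondary instruments. At 0.05/14, f=0.39 has about 68% power with 40 per arm, and the effect detectable at 80% is about f=0.43. So f=0.39 holds only at the protocol's own alpha of 0.01.

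Finally, the protocol does not expressly promise a powered test within each site, and the pilot mismatch does not enter the power calculation. Both are minor, and the main point does not depend on them.

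**Conclusion.** The concern holds. On the stated inputs, with one value per woman and a two-sided test, the primary claim is about 20 percentage points too high and the secondary claim about 35. No reading confined to stated quantities and the planned 100 women reaches both figures. The miss rates of 40% and 55% apply to that single-value analysis; with 20 assessments and a within-person correlation of 0.3 to 0.7, power for the primary would be 97% to 74%.

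This does not show that N=100 is too small. The attrition step is right (40/0.8 = 50), and at d=0.76 the power with 40 per arm is 91.9%. That effect comes from a pilot of 14 people, five of them women, so it cannot stand in for a sound statement about medium effects.

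**What to change.** Keep N=100 and choose one of two corrections to Adequacy of Sample Size.

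1. Restate the sensitivity. For example: with 40 evaluable women per arm and a two-sided test, there is 80% power for f=0.32 at alpha 0.05 and for f=0.39 at alpha 0.01; power is 60% at f=0.25 (alpha 0.05) and 45% at f=0.28 (alpha 0.01).
2. If a repeated-measures or baseline-adjusted model was intended, name it as the analysis model in Data Analysis, say whether f refers to one assessment or to the average, give the number of assessments and the assumed correlation, and show power over a range such as 0.3 to 0.7.

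In either case, state how many secondary tests the alpha of 0.01 covers, and do not present 40 per group as powering Aim 3 within each site. Reconcile the pilot placebo composition in Section II, B.2 with the 40.18%.

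The cost is protocol wording, with no added patients or procedures. The stated sensitivity becomes less favourable unless a model and correlation that support it are specified.

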Laboratory Challenge Component: An identical laboratory challenge session will be conducted in the initial week of outpatient treatment Week 0, prior to medication, and again in Week 9. Our standard imagery script development procedures will be used to develop the stress, drug cue and neutral relaxing imagery scripts. The stress imagery script will be based on participants' description of a recent personal event experienced as "most stressful", and determined as such by rating it above 8 on a 10-point stress scale. These may include breakup with a significant other, marital conflict or job-related stress. A drug cue script will be developed based on situations involving people places and things pertaining to drug use that led to wanting drug and eventual drug use (e.g., meeting drug using friend, going by a favorite bar, etc). The neutral script will be developed from a personal non-alcohol-related relaxing situation. A 5-minute 'script' of each scenario will be written using Scene Construction Questionnaires ([name], 2009) where verbal and non-verbal responses, and physiological and bodily sensations regarding the events will be obtained. A script is then written following standard format and content procedures and scripts are then recorded onto audiotape for guided imagery in the laboratory sessions ([name], 2009). On the morning of the day prior to the initial laboratory session, participants will be brought into the testing room to receive training in relaxation and imagery procedures, as well as familiarize themselves with the subjective rating forms. The 10-min relaxation training will comprise muscle relaxation procedures in order to help subjects reach a relaxed state prior to imagery exposure during the laboratory sessions.

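### No outcome model is stated for the laboratory measures taken at Week 0 and Week 9; the Week 0 value should be a prespecified covariate for Week 9

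*Combined protocol and SAP*

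**What the plan says.** All references are to the Combined protocol and SAP.

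- **Timing.** Section I, item 4 (Laboratory Challenge Component) schedules the same laboratory session twice: "Week 0, prior to medication, and again in Week 9". Each session has a stress, a drug cue and a neutral condition.
- **Treatment contrast.** Section I, item 13 (Adequacy of Sample Size) names a treatment contrast only in its power sentences. For the primary outcome, power is "for the main effect of medication group on the primary outcome variable". For the secondary outcomes, it is stated "with 80% power for all the main effects for secondary outcome variables".
- **Model and covariates.** The Data Analysis paragraph of item 13 gives no outcome model, no group-by-session term and no role for Week 0. Its only covariate rule is conditional: demographic and clinical variables are compared between arms, and a variable is adjusted for if a difference is found.
- **Multiplicity.** "Significance levels for secondary outcomes will be adjusted using Bonferroni correction for number of analyses performed". The power paragraph takes an alpha "level of 0.01 to correct for multiple tests for the secondary outcome measures".

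**The concern.** Aim 1 is target engagement: does guanfacine change provoked craving and cognitive flexibility? For these measures the design supplies a pre-drug value of the same quantity in the same woman under the same condition. The plan leaves two things open.

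First, under the conditional rule Week 0 goes unused whenever the arms look balanced. The value of a baseline covariate comes from its correlation with the outcome, not from imbalance, so the rule discards precision that has already been paid for. It also makes the analysis depend on a baseline test.

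Second, the plan does not exclude a group-by-session analysis in which the group main effect is read as the treatment effect. Such an effect averages a session that cannot contain a drug effect with one that can. At stake is the sensitivity of the laboratory part of Aim 1.

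**Working it through.** **Inputs from the documents (item 13).** 40 evaluable per arm; f = 0.25 at alpha 0.05 (primary); f = 0.28 at alpha 0.01 (secondary). For two equal groups d = 2f, so d = 0.50 and 0.56.

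**Assumptions.** Two-sided tests; equal SD at both sessions; no arm difference at Week 0 beyond chance; one value per woman per session. The Week 0–Week 9 correlation ρ is not given, so a range is shown.

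**The plan's own figures first.** With one value per woman, λ = d² × 40/2, referred to the noncentral F with 1 and 78 df.

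- Secondary: 0.56² × 20 = 6.27, power 45%, against the stated 80%.
- Primary: 0.50² × 20 = 5.00, power 60%. The plan says: "This sample size allows for detection of medium effect sizes ($f=0.25$, Cohen) with more than 80% power".

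Neither figure reproduces. Averaging 20 measures with correlation 0.5 would give 79% and 86%, but the plan states no such number or correlation. That is a separate matter; here the inputs serve only to compare analyses.

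**Standardized effect under each analysis of a two-session measure**

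- Week 9 alone: d
- Change from Week 0 (group-by-session): d/√(2(1−ρ))
- Week 9 adjusted for Week 0: d/√(1−ρ²)
- Main effect over both sessions: (d/2)/√((1+ρ)/2)

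Power uses the square of this effect times 20 as λ, with 78 error df (77 for the adjusted analysis).

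**Worked case, d = 0.50, ρ = 0.5, alpha 0.05**

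- Week 9 alone: λ = 5.00, power 60%.
- Change: 0.50/√1 = 0.50, λ = 5.00, power 60%.
- Adjusted: 0.50/√0.75 = 0.577, λ = 6.67, power 72%.

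**Range**

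| Analysis | d = 0.50, alpha 0.05; ρ = 0.3 / 0.5 / 0.7 | d = 0.56, alpha 0.01; ρ = 0.3 / 0.5 / 0.7 |
|---|---|---|
| Week 9 alone | 60 / 60 / 60% | 45 / 45 / 45% |
| Change score | 46 / 60 / 81% | 31 / 45 / 72% |
| Week 9 adjusted for Week 0 | 64 / 72 / 87% | 50 / 60 / 80% |
| Main effect over both sessions, if used | 28 / 25 / 22% | 15 / 12 / 11% |

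At ρ = 0 the adjusted analysis matches Week 9 alone (60% and 45%), so the lost degree of freedom is immaterial.

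**If Week 0 were made an outcome level.** The raw main effect is (0 + d)/2, exactly half. The standardized effect falls less: it is multiplied by 0.71 at ρ = 0, 0.58 at ρ = 0.5 and 0.51 at ρ = 0.9. A simulation (4,000 runs, d = 0.56, ρ = 0.5, alpha 0.01) gave mean estimates of 0.283 for the two-session main effect and 0.564 for the adjusted analysis, with power 13% and 60%. A measure with one intake value and ten weekly values would keep 10/11 = 0.91 of the raw effect, if the effect is constant over the weeks.

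**Testing each condition separately.** Splitting alpha 0.01 over three conditions gives 0.01/3 = 0.0033. At d = 0.56 and ρ = 0.5 the adjusted analysis then has 45% power, the same as unadjusted Week 9 at 0.01.

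**The case against.** A reader might infer that Aim 1 will be tested by a main effect that averages in Week 0, so that the fix raises power from 25% to 72%. The documents do not support that:

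- Both main-effect phrases stand in power sentences, and no repeated-measures model with Week 0 as an outcome level appears anywhere.
- Section II.B, item 2 reports a drug-group main effect from an earlier laboratory study whose described sessions all took place after titration, at full dose. There the term includes no pre-drug value. The same text reports interactions, so naming main effects for power does not mean that nothing else will be tested.
- The 40 per cell is justified for the clinical outcome hypotheses of Aims 2 and 3. Laboratory visual-analog craving is listed under Laboratory Challenge Assessments, apart from the secondary outcomes. Stroop is both a listed secondary outcome and a laboratory task.
- The primary urine outcome is collected within the 10 weeks and has no Week 0 level.

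All of this stands, so the fair comparators are Week 9 alone and change scores.

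It can also be said that the covariate rule might admit Week 0. It might, but only after a baseline difference is found, and the plan does not say whether Week 0 laboratory values are among the variables compared. That is not prespecified adjustment.

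**Conclusion.** The point holds as an unspecified model and an unused baseline, not as a documented choice of a wrong test. At 40 per arm, d = 0.50, alpha 0.05 and an assumed correlation of 0.5, prespecified adjustment raises power from about 60% (Week 9 alone or change) to 72%. Over correlations of 0.3 to 0.7 it reaches 64% to 87%. At d = 0.56 and alpha 0.01 it gives 50% to 80%, against 45% for Week 9 alone. The gain rests on the assumed correlation and on one medication test per measure.

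Halving is a risk that the wording leaves open. It concerns the raw effect of two-session measures only; for weekly measures with one intake value the loss would be about 9%. The change should be made because Aim 1 benefits at almost no cost, but the primary analysis does not depend on it.

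**What to change.** Add to item 13, Data Analysis:

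1. Laboratory craving and Stroop are compared between arms at Week 9, in one model per measure across the imagery conditions. The same woman's Week 0 value for that condition is a covariate, whatever any baseline comparison shows.
2. Each measure has one medication test. The conditions that it averages over are named in advance, and condition-specific estimates are descriptive. This keeps the Bonferroni count from tripling.
3. Week 0 is never an outcome level in a medication main effect.
4. Clinic measures with an intake value, such as the Perceived Stress Scale, use that value as a covariate in the same way.

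The cost is SAP wording and one degree of freedom for the covariate. No new data, visits or participants are needed. The price of a single test is that an effect confined to one condition is diluted in the average, which is why the averaged conditions must be fixed beforehand.
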